**PLEASE NOTE that the research may be funded by VA, by other sponsors, or may be unfunded.**

## Summary of Required Reviews (other than IRB)

**1 Additional Committee Reviews** - Based on your responses to the previous questions, you have identified the following additional reviews. To complete or view these additional committees' forms, click on the links below or exit this application and click on the appropriate button on left side of this submission's webpage.

Name of Related Submission

*This protocol has no related submissions (RSC, GCRC, IBC, etc)*

**2 Required Department and Specialty Reviews** - Based on the PI's organization (department, division, etc.) affiliation and answers to previous questions (use of Cancer Center, etc.), the organizations listed below are required to review this application. These reviews are conducted online and no additional forms or steps by the study team are required.

Name of Organization

Psych CMHSR General

**Review Status**

Complete

ID: VIEW4E1C8D9AE4000

Name: v2\_Summary of Required Reviews (other than IRB)

## Additional Documents

1 Upload all additional documents here:

| Name                                                                   | Created             | Modified Date       |
|------------------------------------------------------------------------|---------------------|---------------------|
| Sub Study Kenya Informed consent form (English and Swahili).docx(0.01) | 2/24/2021 1:07 PM   | 2/24/2021 1:07 PM   |
| Formative sessions_Swahili consent V1.0.pdf(0.01)                      | 10/4/2019 8:21 AM   | 10/4/2019 8:21 AM   |
| Formative Interview 8.14.19.pdf(0.02)                                  | 11/13/2018 12:54 PM | 9/17/2019 8:53 AM   |
| Other Sites Where Research Activities Will Be Conducted (3).docx(0.02) | 10/4/2018 1:08 PM   | 11/14/2018 11:10 AM |
| Formative Focus Group.doc(0.01)                                        | 11/13/2018 12:54 PM | 11/13/2018 12:54 PM |
| Smoking Kenya Consent - Feedback Sessions.doc(0.01)                    | 11/13/2018 9:29 AM  | 11/13/2018 9:29 AM  |
| [name] certificate(0.01)                                           | 10/24/2018 8:54 AM  | 10/24/2018 8:54 AM  |
| [name] CITI 2018.pdf(0.01)                                           | 1/16/2018 10:31 AM  | 1/16/2018 10:31 AM  |
| HIV Smoking Consent Form - Kenya (1).doc(0.03)                         | 12/20/2017 7:34 AM  | 1/16/2018 8:52 AM   |
| [name]'s Certificates(0.01)                                     | 11/7/2017 11:04 AM  | 11/7/2017 11:04 AM  |
| STaff Certificates.pdf(0.01)                                           | 10/18/2017 8:24 AM  | 10/18/2017 8:24 AM  |
| HIV Study Schedule 2017 KENYA.docx(0.02)                               | 10/17/2017 3:02 PM  | 10/18/2017 8:02 AM  |
| SI HI Checklist Kenya.docx(0.01)                                       | 10/18/2017 7:57 AM  | 10/18/2017 7:57 AM  |
| PSF.Curriculum.DSR.2015 MODIFIED.docx(0.01)                            | 10/17/2017 2:56 PM  | 10/17/2017 2:56 PM  |
| Brochure for Control Group.pub(0.01)                                   | 10/17/2017 2:54 PM  | 10/17/2017 2:54 PM  |
| Questions of Understanding.docx(0.01)                                  | 10/17/2017 2:54 PM  | 10/17/2017 2:54 PM  |
| Contraception Consent Form.docx(0.01)                                  | 10/17/2017 2:53 PM  | 10/17/2017 2:53 PM  |
| Package Insert for Bupropion.docx(0.01)                                | 10/17/2017 2:52 PM  | 10/17/2017 2:52 PM  |

ID: VIEW4E0962513A000  
Name: v2\_Additional Documents

## Final Page of Application

**You have reached the final page of this application.** It is recommended that you click on the "Hide/Show Errors" link on the upper or lower breadcrumb row of this page. The "Hide/Show Errors" will do a search of your application, and highlight areas that are required or need to be completed prior to submitting.

By submitting this application, you are electronically routing the protocol for departmental scientific review and all other necessary reviews. According to information you have provided, this application will be routed to the following Departments for review prior to being forwarded to the IRB for review. These reviews are conducted online and no additional forms or steps by the study team are required.

| Name of Organization | Review Status |
|----------------------|---------------|
| Psych CMHSR General  | Complete      |

**Required Safety Committee Reviews** - In addition to the IRB, the following committees must review this submission. Each additional committee has a separate online form that the study team will be required to fill out. All committee applications (IRB plus those listed here) must be completed properly before the 'package' of applications can be submitted. The team may complete these additional forms in any order or at any time prior to submission of the IRB Application. To complete or view these additional committees' forms, click on the links below or exit this application and click on the appropriate button on left side of this submission's Workspace.

Name of Related Submission

*This protocol has no related submissions (RSC, GCRC, IBC, etc)*

You may check the progress of your application at any time by returning to the Workspace of this submission. A detailed history, including notes, dates, and times of events, is provided to you for this purpose.

If a reviewer returns the application to you, you must address their concerns and resubmit the protocol for review to all designated departments. After all departments have reviewed the application, it will automatically be sent to the IRB for review. Changes made to the submission after its approval must be submitted as modifications.

*** Full Title: Optimizing smoking cessation interventions for PLWH in Nairobi, Kenya**

STATISTICAL ANALYSIS PLAN

Power Calculations: With a total of 300 participants and an estimated 20% attrition, we expect 60 participants per cell in the factorial design. This will provide a total of 120 participants per main effect condition (Drug or Psychosocial Intervention). All power analyses were conducted with a two tailed alpha of .05 and powerset to .80. With the expected sample and the anticipated retention rate, the study's 2 main effects((1) bupropion vs. placebo; (2) PSF versus SOC) are each powered to detect a Cohen's h of from .28 to .36 (small effect)98. In addition, we will be able to determine if there is a significant additive effect (i.e. whether the combination of bupropion and PSF is significantly better than either treatment alone). For this comparison we have sufficient power to detect an effect size of $h = .39 - .49$ (small to medium effect). The evaluation of the exploratory interaction Aim is a possible but not necessary benefit of a factorial design that could determine whether the combination of the two treatments provides more than a simple additive effect. The interaction effect is powered to detect a Cohen's d of .9 (large effect)98. Power was calculated using the PASS software. (Version 13, Logistic Regression Procedure.)

Overview of Analytic Methods: The primary study analyses will adopt an intent-to-treat strategy. Data will be screened for errors using frequency and contingency tables and univariate and bivariate plots before formal analysis. These plots and summaries will allow us to be cognizant of data distribution characteristics before building regression models. To assess indication of self-selection bias, we will compare the demographic characteristics of the participants that agreed to participate in the study to those who were approached, but were not interested in participating.

Covariate Selection: We expect, due to randomization and sufficiently large sample size, that demographic, clinical characteristic, and outcome variables at baseline in the four conditions will not be significantly different. However, we will perform tests for differences (imbalances) on demographic (e.g. age, race, gender) and other potential confounder variables across the four groups. Imbalances may occur in spite of the randomization procedure. If there are important variables significantly out of balance we will add them as covariates in the models. In addition, all models will include covariates indicating whether the participants are using HAART.

Missing Data: Missing data can arise from active refusal and from participants who cannot be located. Attrition will be carefully monitored. We will attempt to assess all participants at follow up regardless of whether they engage with smoking cessation services during the study (intent-to-treat). To assess the potential confounding effects of missing data, we will compare the baseline characteristics of participants who do and do not complete the 12- and 36-week assessments. If we find significant differences between dropouts and completers and differential attrition, we will include any potential confounding variables as covariates. If a subject fails to complete interim visits, we will attempt to re-engage him/her for the 36 week visit in order to ascertain the primary abstinence endpoint. If a subject refuses to be contacted or otherwise loses contact with the investigators, we will censor data at the point of loss and the subject will be considered non-abstinent. In addition, the investigative team will agree by consensus on a set of rules to guide the imputation of missing data.

values in the various study scales. If necessary, we will conduct a sensitivity analysis to investigate how estimates/results change over a range of several plausible assumptions regarding the missing mechanism together with multiple imputations to most accurately capture existent random variability. Multiple Comparisons: We will use the sequential Bonferroni-type procedure for dependent hypothesis tests⁹⁹ to control the false discovery rate (the expected (or on average) proportion of falsely rejected hypotheses) at 5%. Primary Aims: We will use separate logistic regression models (SAS, 9.3: Proc Logistic) at each post baseline time point to assess the main effects of bupropion vs. placebo (Drug) and PSF vs. SOC (Beh) on smoking cessation. In addition, we will assess any covariates that were identified above. The test of the hypotheses will be the test of whether the coefficients for the main effects are significantly different from 0 based on the likelihood ratio test. To assess if the combination of bupropion and PSF is significantly more effective than either of the treatments alone, we will create an indicator variable for these 3 conditions with the combined treatment as the reference. The analysis will proceed as described above.

Exploratory Analyses: Other smoking outcomes: We will use a Generalized Linear Mixed Model (GLMM; Proc MIXED) to assess if the treatment conditions have a significant effect on other smoking outcomes (e.g. number of cigarettes smoked per day) over time. Treatment conditions, time and the interaction of time with the treatment conditions will be included in the model. A random intercept will be used to account for the nonindependence of the repeated measures. An unstructured covariance matrix will be employed. Significant effects will be followed up with specific contrast statements. Mediation: We will use Proc Mixed to assess the interventions impact on possible mediating variables for bupropion (craving, withdrawal) and for PSF (self-efficacy, depression, loneliness, substance abuse, and dosage of the PSF intervention (number of sessions completed)). Mediators will be assessed at 12 weeks, controlling for baseline. For those variables that are significant we will conduct additional analyses to determine if change in those mediators is related to smoking cessation at 36 weeks. If all conditions are met, we will use the MacKinnon 100 approach to formally assess for mediation of smoking cessation by the targets of the interventions. Moderators: We will assess possible clinical (e.g. depression, smoking severity at baseline, years smoked, etc.) and demographic moderators on smoking cessation. We use the analyses described for the primary aim to assess moderation by including these variables and their interaction with the treatment conditions to the models

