**1 \* Describe the purpose, specific aims, or objectives of this research. State the hypothesis to be tested:**

Primary Aim 1: Compare bupropion therapy to placebo on rates of 7-day point prevalence abstinence (PPA) at 36 weeks in smokers with HIV/AIDS. We hypothesize that rates of smoking abstinence at week 36 will be higher in those treated with bupropion compared to placebo.

Primary Aim 2: Compare Positively Smoke Free to low intensity, brief counseling on rates of 7-day PPA at 36 weeks in smokers with HIV/AIDS. We hypothesize that rates of smoking abstinence at week 36 will be higher in those treated with Positively Smoke Free compared to brief counseling.

Primary Aim 3: Compare Positively Smoke Free + bupropion to the other two study conditions outlined above on rates of 7-day PPA in smokers with HIV/AIDS at 36 weeks. We hypothesize the effect of Positively Smoke Free with bupropion therapy is greater than the effect of Positively Smoke Free or bupropion therapy alone.

Secondary Aim: Estimate the organizational costs of implementing Positively Smoke Free, bupropion or both. All cost estimates will be appropriately time-discounted and inflation-adjusted. The planned assessment will yield rigorously obtained approximations of total implementation costs at a new site of care.

Exploratory Aim: Explore whether the effect of PSF compared to brief counseling with bupropion is greater than the effect of PSF without bupropion.

Given the critical need for information about the up-front expenses required to implement smoking cessation services in Kenya, we plan to conduct an implementation costs assessment to provide rigorously obtained approximations of total implementation costs of each intervention tested in this trial.

Sub Study:

AIM 1: Develop, culturally adapt and update the PSF intervention in the main study to include educational material about the cancer risk associated with tobacco and alcohol use.

AIM 2: Preliminarily determine the extent the updated PSF syllabus changes awareness of the link between alcohol and tobacco use and cancer.

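### The lower ends of the SAP's detectable effects (h = .28 for the main effects, h = .39 for the combination) do not follow from its stated sample size, alpha and power

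*SAP*

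**What the plan says.** The SAP, under Power Calculations, starts from 300 participants and 20% attrition, which leaves 60 per cell. It continues: "This will provide a total of 120 participants per main effect condition". It also states: "All power analyses were conducted with a two tailed alpha of .05 and powerset to .80". On that basis the two main effects (bupropion vs placebo, Positively Smoke Free vs standard of care) "are each powered to detect a Cohen's h of from .28 to .36 (small effect". The sentence ties this range to the sample expected after attrition.

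For the combination against either treatment alone, it says "For this comparison we have sufficient power to detect an effect size of" h = .39 to .49. No sample size is given for this comparison, and nothing explains what the two ends of either range represent. The software is named (PASS 13, logistic regression) but not its settings.

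Two other places bear on the combination contrast. Under Primary Aims, the SAP says "we will create an indicator variable for these 3 conditions with the combined treatment as the reference", which implies the combined arm against each single-treatment arm. Primary Aim 3 in the Protocol is looser: "Compare Positively Smoke Free + bupropion to the other two study conditions outlined above". That leaves room for a pooled contrast.

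**The concern.** Cohen's h is a difference of arcsine-transformed proportions, a scale on which the variance hardly depends on the underlying rates. Once the group sizes, alpha and power are fixed, there is essentially one detectable h. A range therefore needs some input to vary, and the SAP names none. The lower ends look too small for groups of 120 and 60.

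This section is where a reader learns what the primary comparisons can detect at 80% power. If .28 is wrong, a null main effect could be taken to rule out effects that the trial would in fact miss about 4 times in 10. The same applies to .39 for the combination, which is a primary aim.

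**Working it through.** **Inputs.** Two-tailed alpha .05 (z = 1.960), power .80 (z = 0.842), 60 per cell and 120 per main-effect condition (SAP, Power Calculations). Allocation is 1:1:1:1 (Protocol, Study Procedures, Randomization). The combination contrast is 60 vs 60 under the SAP's three-level indicator, or 60 vs 120 if the single-treatment arms are pooled.

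**Formulas.**
- Detectable h = (1.960 + 0.842) × √(1/n₁ + 1/n₂)
- Power at h = Φ(h / √(1/n₁ + 1/n₂) − 1.960)
- n per equal group for 80% power = 2 × (2.802 / h)²

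**Main effects, 120 vs 120.** √(1/120 + 1/120) = 0.1291.
- Detectable h = 2.802 × 0.1291 = .362. This reproduces the SAP's upper end.
- At .36: .36 / 0.1291 − 1.960 = 0.829, power 79.6%.
- At .28: .28 / 0.1291 − 1.960 = 0.209, power 58.3%.
- n for .28 = 2 × (2.802 / .28)² ≈ 200 per condition, or 400 analysed in a trial of 300.

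**Combination, 60 vs 60.** √(1/60 + 1/60) = 0.1826.
- Detectable h = .511.
- At .39: power 57.0%. At .49: power 76.5%.
- n for .39 ≈ 103 per cell.

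**Combination pooled, 60 vs 120.** √(1/60 + 1/120) = 0.1581.
- Detectable h = .443.
- At .39: power 69.4%. At .49: power 87.3%.

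**Is the arcsine approximation to blame?** The power of the unadjusted two-group likelihood ratio test was also enumerated exactly. Comparator rates of 5–25% were assumed, since the SAP gives none.

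| Contrast | h | Arcsine power | Exact power |
|---|---|---|---|
| 120 vs 120 | .28 | 58.3% | 58.3–59.0% |
| 120 vs 120 | .36 | 79.6% | 79.8–80.2% |
| 60 vs 60 | .39 | 57.0% | 57.0–59.1% |
| 60 vs 60 | .49 | 76.5% | 76.5–78.2% |
| 60 vs 120 | .39 | 69.4% | 69.6–70.8% |
| 60 vs 120 | .49 | 87.3% | 87.4–88.0% |

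Varying the base rate therefore does not produce the range. Across two-sided logistic and two-proportion forms, no variant at 120 vs 120 gave a detectable h below about .35.

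**Would another choice of inputs recover the lower ends?**
- One-sided .05 at 120 vs 120: detectable h = (1.645 + 0.842) × 0.1291 = .321.
- Two-sided with no attrition, 150 vs 150: detectable h .323, power 67.9% at .28. At 75 vs 75, power at .39 is 66.6%.
- To come within two points of 80%, .28 needs both a one-sided test and no attrition (78.2%). A value of .39 needs pooling plus either a one-sided test (60 vs 120, 79.4%) or no attrition (75 vs 150, about 79%).

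Each of these changes an input that the SAP states.

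**The case against.** The .28 figure has no real defence. The best case concerns .39. The SAP adopts intent-to-treat and, under Missing Data, says that after loss of contact "the subject will be considered non-abstinent". The abstinence analysis could then include all 300, that is 75 per cell. Combined with a pooled reading of Aim 3, 75 vs 150 gives a detectable h of about .396 and about 79% power at .39, nearly as close as the 79.6% accepted above for .36.

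This shows where .39 might have come from, but it does not make the stated figure right. The Power Calculations section names 60 per cell, and the Primary Aims indicator points to pairwise contrasts. Counting lost participants as non-abstinent also shrinks both rates. If 20% are lost equally in all arms, so that rates are multiplied by 0.8 (an assumption; comparator rates 5–20%), the detectable h on the undiluted scale is:
- .366–.376 for 150 vs 150
- .519–.536 for 75 vs 75
- .449–.462 for 75 vs 150

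None improves on .362, .511 and .443. The SAP does not say on which scale its h is expressed. If it is the analysed endpoint with lost counted as smoking, the miss rate is nearer 1 in 3 (67.9% power at .28, and 66.6% at .39 pairwise), which is still short of 80%.

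A second objection limits the consequence, and it stands. The Protocol's Sample Size section plans on 10% vs 25% and 7% vs 20%, which are h of about .40 and .39. Both exceed .36 and have about 88% and 86% power at 120 vs 120, provided those rates hold for the pooled conditions. The trial is not shown to be underpowered for the main effects it was designed around.

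Third, the simple figures ignore the covariates that the SAP adds to the models. That is true, and it is a reason to label them as unadjusted.

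**Conclusion.** The concern holds. At the stated n, alpha and power, the detectable h for each main effect is .36. The lower end of .28 has about 58% power. For the combination, .39 has about 57% power in the pairwise contrast that the SAP describes and about 69% if pooled, so it fails on both readings at 60 per cell. The upper end of .49 is slightly short pairwise (about 77%, with .51 needed) and is met if pooled (about 87%).

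The .28 result is the firmer of the two: it rests only on inputs the SAP states. The .39 result also depends on holding to 60 per cell, as the SAP says. All figures are for unadjusted two-group comparisons, before the false discovery rate procedure in Multiple Comparisons. The effect is confined to planning statements and to how a null result is read.

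**What to change.** In the SAP's Power Calculations, state at two-tailed alpha .05 and 80% power:
- h = .36 for each main effect (120 vs 120).
- h = .51 for the combination against each single treatment (60 vs 60). If a pooled contrast is intended, declare it, make Primary Aims agree, and state h = .44 (60 vs 120).

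Delete .28 and .39. Do not move to an all-randomised n to keep them: with lost participants counted as non-abstinent, the larger n brings no gain under the equal-loss assumption above. Say that the figures are unadjusted for covariates and for the false discovery rate procedure. An adjusted value cannot be given until the family of tests is stated.

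The cost is an edit to the text, with no change to sample size, tests or estimates. The stated sensitivity becomes less favourable.

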**1 \* Provide the rationale and sample size calculations for the proposed target population:**

With a total of 300 participants and an estimated 20% attrition, we will have 60 participants per cell in the factorial design. This will provide a total of 120 participants per main effect condition (Drug or Psychosocial Intervention). Meta analyses of bupropion vs. placebo in the general population estimate the effect as an increase in abstinence from 10% with placebo to 25% with bupropion. The effect for PSF compared to SOC without any drug intervention is estimated to be an increase from 7% to 20%. Using a logistic regression model with alpha equal to .05 (two tailed) we will have greater than 80% power to detect these main effects. We will assess whether the combination of PSF and bupropion will have a simple additive effect on smoking abstinence (no interaction) or synergistic effect on smoking cessation (interaction). We will have 80% power to detect a 10% increase in relative abstinence when PSF is compared to SOC without bupropion to PSF compared to SOC with bupropion. Power was calculated using the PASS software. (Version 13, Logistic Regression Procedure.)

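### On the SAP's own inputs, each contrast of the combination with a single treatment detects h of about .51, so the lower end of the stated .39 to .49 is unsupported and the upper end is a near miss.

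*SAP*

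**What the plan says.** The protocol lists the comparison of the combination with each single treatment as Primary Aim 3, tested on 7-day abstinence at week 36.

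The SAP's Power Calculations start from 300 randomised and 20% attrition: "we expect 60 participants per cell in the factorial design". They continue: "All power analyses were conducted with a two tailed alpha of .05", with power set at .80. The two main effects "are each powered to detect a Cohen's h of from .28 to .36". For the combination against either treatment alone the SAP says: "For this comparison we have sufficient power to detect an effect size of $h = .39 - .49$ (small to medium effect".

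The SAP's Primary Aims text gives the analysis. "To assess if the combination of bupropion and PSF is significantly more effective than either of the treatments alone", it fits a three-level indicator with the combined arm as the reference.

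Two other parts of the SAP affect the figure. Under Missing Data, for a participant who is lost, "we will censor data at the point of loss and the subject will be considered non-abstinent". Under Multiple Comparisons, "We will use the sequential Bonferroni-type procedure for dependent hypothesis tests", with the false discovery rate held at 5%.

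**The concern.** A contrast between two single cells uses half as many participants per side as a main effect, so its detectable h should be larger by a factor of the square root of 2. The SAP's upper main-effect value, .36, scales to .36 × 1.414 = .51, which lies above the whole range given for the combination. The lower value, .39, is close to .28 × 1.414 = .396, but that helps only if .28 is itself detectable with 120 per side.

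Aim 3 is one of three primary aims. If the stated range is taken at face value, a non-significant result could be read as evidence that the combination adds nothing, when a contrast at the lower end of the range had little better than an even chance of reaching significance.

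**Working it through.** **Inputs.** Two-sided alpha .05 (z = 1.960), 80% power (z = 0.842) and 60 per cell (300/4 = 75; 75 × 0.8 = 60), all from the SAP's Power Calculations. The contrasts come from the SAP's Primary Aims text.

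**Formulas.** SE = √(1/n1 + 1/n2). Detectable h = (1.960 + 0.842) × SE. Power = Φ(h/SE − 1.960).

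**Step 1: reproduce the SAP's main-effect figure.** At 120 v 120, SE = √(2/120) = .1291 and detectable h = 2.802 × .1291 = .362. This matches the SAP's .36, so the formula agrees with the plan. The lower value, .28, has power Φ(.28/.1291 − 1.960) = Φ(0.21) = 58%. It is not detectable at 80% and cannot justify .39.

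**Step 2: the Aim 3 contrast as planned.** At 60 v 60, SE = √(2/60) = .1826.
- Detectable h = 2.802 × .1826 = .511.
- At h = .39: Φ(2.136 − 1.960) = Φ(0.176) = 57%.
- At h = .49: Φ(2.684 − 1.960) = Φ(0.724) = 77% (76.5%).
- Participants per cell for 80% power, 2 × (2.802/h)²: about 104 at .39 and 66 at .49.

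Exact likelihood-ratio power at 60 v 60, with single-treatment rates from 7% to 40%, is 57–59% at .39 and 76.5–78% at .49.

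**Step 3: other readings of the inputs.**

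| Reading | Detectable h | Power at .39 | Power at .49 |
|---|---|---|---|
| 60 v 60, two-sided (SAP inputs) | .511 | 57% | 77% |
| 75 v 75, losses counted as smoking, before dilution | .457 | 67% | 85% |
| 2-df test across the three arms, 60 per cell, equal single arms | .491 | 59% | 80% |
| Combination v pooled single arms, 60 v 120 | .443 | 69% | 87% |
| Combination v pooled single arms, 75 v 150 | .396 | 79% | 93% |

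The 2-df row uses noncentrality n × h² × 2/3; at n = 60 and h = .49 that is 9.6.

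Dilution matters in the 75-per-cell row. Assume h = .49 among those followed up, 20% loss in each arm and 20% abstinence on PSF alone. Counting losses as smoking then turns 20% v 42.4% into 16% v 33.9%. The h falls to about .42, and power at 75 per cell is 73%.

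**Step 4: size on the abstinence scale.** Take 20% on the single treatment (the protocol's planning rate for PSF without drug) and use p = sin²(arcsin√.20 + h/2). Then h = .39, .49 and .51 correspond to about 37.5%, 42% and 43% abstinent on the combination.

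**Step 5: conditional on a rule that both contrasts must succeed.** With equal effects and a correlation of .5 from the shared combination arm, 80% power for both needs h = .57 at 60 per cell (.51 at 75). Joint power at 60 per cell is 41% at .39 and 64% at .49. If the single arms were 20% and 25%, they would differ by h = .12, and the harder contrast would need about .53.

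**Step 6: multiplicity.** The SAP does not define the family of tests. If it is assumed to be the three primary aims under Benjamini–Yekutieli, the thresholds are .05 × k/(3 × 1.833) = .0091, .0182 and .0273. The detectable h per contrast at 60 per cell is then about .63, .58 and .56.

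**The case against.** The best defence concerns the upper end. At .49 the shortfall is 2 to 4 percentage points of power. A log-odds approximation, closer to the logistic procedure the SAP cites, gives a detectable h of .48 to .49 at base rates of 7–10%. A 2-df likelihood-ratio test gives .491, and a three-level indicator with a likelihood-ratio test can be read that way, although such a test would not show superiority over each single arm. Analysing all 75 per cell covers .49 before dilution. All of this stands, so a reader who infers that the whole range fails equally goes too far.

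At .39 the defence fails. The only two-sided reading that comes near it pools the single arms at 75 v 150. That drops the SAP's 60 per cell, is not the analysis the SAP describes, and cannot show superiority to each treatment. One-sided testing at 60 v 120 gives .393 but contradicts the two-tailed alpha.

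Two stronger readings are tempting. A reader might hold the SAP to .57, since the documents speak of beating either treatment alone. No decision rule requiring both wins is written, and .57 also assumes equal effects, so it cannot be set against the SAP as its own criterion. A reader might also conclude that the trial needs more participants, or that Aims 1 and 2 are affected. The combination figure does not bear on those aims, and the protocol keeps the main study at 300.

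The protocol's sample-size text approaches the combination through the interaction ("We will assess whether the combination of PSF and bupropion will have a simple additive effect on smoking abstinence (no interaction"). That is a separate inconsistency and does not change this arithmetic.

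**Conclusion.** The stated range does not follow from the SAP's inputs. With 60 per cell and two-sided .05, each combination contrast detects h of about .51 at 80% power. The .39 end is unsupported, at about 57% power. The .49 end is a near miss at about 77% and is reached under some reasonable readings. With 75 per cell the figure is about .46 before dilution, and power at .39 is still only 67%.

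These results rest on the arcsine approximation, which reproduces the SAP's .36 and agrees with exact likelihood-ratio power, and on no multiplicity adjustment. The .57 figure holds only if both contrasts must succeed and their effects are equal. This is an error in a power statement for a primary aim. It affects how a null Aim 3 is read, not the design.

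**What to change.** In the SAP's Power Calculations:
- Replace the range for the combination with h of about .51 per contrast at 60 per cell, or about .46 at 75 per cell before dilution.
- Name the analysis set the figure refers to: those followed up, or all randomised with losses counted as smoking.
- State that the figure is before the planned false discovery rate adjustment, which raises the detectable effect.
- State whether Aim 3 requires superiority over both single treatments. If it does, also report about .57 at 60 per cell, assuming equal effects, and note that the value on the harder contrast is lower if the single arms differ.

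The cost is a few sentences. No data, participants or change of sample size are needed. The stated sensitivity for Aim 3 becomes less favourable but accurate.
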